9.4.3 Handling of missing values/censoring/discontinuations

Patients who withdraw early will be replaced, as described in Section 5.5.9. The following two data sets may be analyzed separately: data set 1 will include all patients' data without any surgery throughout the trial; data set 2 will include data set 1 and patients' data prior to surgery. Data post-surgery will not be used for primary analysis.

9.4.4 Supportive analyses

Part A

As a supportive analysis, log ratio to baseline of tumor volume at week 4 may be subjected to an Analysis of Covariance (ANCOVA) model. The model will include log transformed tumor volume at baseline and a factor for treatment. Point estimates and 95% confidence interval will be calculated for each treatment group and for the difference of means between treatment groups. Results will then be transformed back to the original scale.

Part B

To study the time course of tumor volume reduction from baseline, a repeated measures ANCOVA model may be fit by resetting the tumor volume at week 4 as baseline for patients in treatment group 2 and the assessment time will be adjusted accordingly. The model will include tumor volume at baseline and assessment time (in month) as fixed effects. Standard fit statistics will be used to determine the best variance-covariance structure. Point estimates and 95% confidence interval will be calculated at each assessment time-point and between different assessment time-points.

Part C

As a supportive analysis, log ratio to baseline of tumor volume at week 4 may be subjected to an Analysis of Covariance (ANCOVA) model. The model will include log transformed tumor volume at baseline and a factor for treatment. Point estimates and 95% confidence interval will be calculated for each treatment arm and for the difference of means between treatment groups. Results will then be transformed back to the original scale.

Parts A, Part B and Part C

A basic dose-time-response model (Lange and Schmidli 2015) will be used to analyze tumor response data from Parts A, B, and C. Time-dose-response models describe and predict drug effect for complex dosing regimens. The mechanistic non-linear regression model used will allow for both inference on model parameters and prediction of the time-changing tumor response for the dosing regimens used in this study. Mechanistic models are based on prior knowledge and provide more reliable predictions. To this end, a Bayesian approach (using prior information) with weakly informative prior will be used. Point estimates and 95% confidence intervals of the model parameters, i.e., the expected response after multiple doses, will be generated using the Emax model. The Emax model will estimate tumor reduction from baseline at each dose and timepoint. Dose-time-response curves based on the model will be generated and graphically presented. The pooled dataset should result in approximately 19 patients on 10mg/kg, 6 patients each on 3 and 5 mg/kg (up to 10 if a lower efficacious dose is identified), and 5 patients (2 in Part A and 3 as first dose in Part B) on placebo.

9.5 Analysis of secondary variables

The first 4 weeks data from Part A, Part B, and Part C will be pooled together for analyses. In addition, data in Part B will be analyzed by treatment groups; we may also pool treatment groups by matching the 1st dose of MCS110 in treatment group 1 to the 2nd dose (1st of MCS110) in treatment group 2.

Part C analyses of secondary variables will be done by treatment group. We may also pool treatment groups across Parts B and C to analyze secondary variables.

9.5.1 Efficacy / Pharmacodynamic variables

Soluble form of M-CSFR (sCSF-1R), bone marker serum C-terminal Type I Collagen peptide (CTX-I) and monocytes (hematology) will be collected as specified in the study assessments schedule.

Summary statistics and graphical display of these parameters over time with the absolute values, and ratio from baseline will be produced. Total circulating M-CSF levels (if available) will be displayed graphically.

Summary statistics and graphical display of this parameter over time with the absolute values, and ratio from baseline will be produced by plasma and synovial fluid separately.

Joint range of motion

Summary statistics and graphical displays for the absolute values, absolute changes from baseline joint range of motion over time will be produced by flexion and extension separately and by each joint type.

Joint Specific Questionnaires

Data will be summarized and graphically displayed similarly by tumor locations.

Corporate Confidential Information

Health-related quality of life

All data related to health-related quality of life including but not limited to EQ5D, mHAQ, will be summarized and graphically displayed similarly.

Pain assessment (VAS)

Pain assessment data will be summarized and graphically displayed similarly.

Time to surgery

Number of patients who receive surgery will be presented and their time to surgery will be listed and summarized accordingly.

Tumor relapse / re-growth

Number of patients who experience recurring PVNS tumor / tumor growth of residual tumor may be listed and their time to relapse /re-growth may be listed and summarized accordingly. The tumor size monitored by MRI will be recorded over time.

Corporate Confidential Information

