2.8 Secondary objectives Part C

- To characterize the PK of multiple doses of MCS110 in PVNS or GCTTS patients.
- To assess pharmacodynamic effects of MCS110 on:
 - total circulating M-CSF levels in PVNS or GCTTS patients.
 - serum C-terminal Type I Collagen peptide (CTX-I), a biomarker of bone resorption.
- To assess the immunogenicity of MCS110 in this population.
- To assess the duration of clinical response, if any, by joint range of motion.
- To assess the degree of functional recovery using questionnaires.
- To assess joint pain using a visual analog scale (VAS).
- To assess time to surgery.
- To assess time to relapse (based on MRI).

3 Investigational Plan

[figure not shown]

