- Part C (arm 10mg/kg): the tumor response to treatment is <45 % of tumor volume reduction after the 3rd dose [determined by MRI at week 12] and MCS110 was tolerated: the patient can receive 1 additional dose of 10 mg/kg

New treatment course in case of recurrence of tumor or regrowth of residual tissue

If, based on MRI, relapse is identified, it is possible to start an additional course of 6 consecutive doses of MCS110 10 mg/kg, if there was:

- Good tolerability of MCS110 during the first treatment cycle
 - Patient received 6 doses
 - No early treatment discontinuation

- Good response in tumor volume reduction: Tumor volume reduction at (up to) 1°EP (8 wks post last dose of 6 doses) of >50% during the 1st treatment cycle
- Relapse defined as:
 - Symptoms (pain, swelling, redness, stiffness) and
 - Tumor volume increase greater than 50% of the difference between tumor volume at BL and the lowest tumor volume measured by MRI.
- Last dose of MCS110 was at least \geq 6 months ago.
- Inclusion/exclusion criteria are still fulfilled.

During the second treatment course safety monitoring will be the same as during the first treatment course. Efficacy will be assessed by MRI after the 3rd dose at week 12 to decide on dosing beyond 4 doses and then again 8 weeks post last dose. Once a lower dose with same efficacy as 10 mg/kg has been identified in Part C, relapse patients will receive the lower dose treatment. During the second treatment course no placebo dose will be administered.

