7.2.7 Time to surgery – listed for Parts B and C only

Patients with their time to surgery will be listed by Part and treatment groups as defined in Section 7.1. Time to surgery is the time from first dose to surgery.

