7.2.8 Time to relapse – listed by Part

Patients who experience recurring PVNS tumor / tumor growth of residual tumor and their time, location, etc. to relapse /re-growth will be listed by Part and treatment group.

Corporate Confidential Information

Corporate Confidential Information

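### Time to surgery and time to relapse are planned only as event-only summaries or listings, with no censoring rule, and the relapse endpoint has no single definition

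*Protocol*

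**What the plan says.** Protocol 2.5 and 2.8 make both times secondary objectives of Parts B and C, and the synopsis lists them among the key secondary objectives.

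**Analysis.** Protocol 9.5.1, on surgery: "Number of patients who receive surgery will be presented and their time to surgery will be listed and summarized accordingly". On relapse it is permissive: "their time to relapse /re-growth may be listed and summarized accordingly". The SAP goes no further than listings. Section 7.2.7 says "Patients with their time to surgery will be listed by Part and treatment groups as defined in Section 7.1", and Section 7.2.8 says of patients with recurrence or regrowth that "their time, location, etc. to relapse /re-growth will be listed by Part and treatment group".

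**Origin.** SAP 7.2.7: "Time to surgery is the time from first dose to surgery". SAP 7.2.8 gives no origin for relapse.

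**Censoring.** Protocol 9.4.3 and SAP 7.1.1 carry the word in their headings. Their text covers replacement of withdrawals, post-surgery data in the primary analysis and non-imputation of missing data. Neither says what to do with a patient who has no event.

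**Follow-up.** Protocol 3.2.1 and 3.2.3 give up to 2 years for Part B and for Part C under Amendment 6, and 1.5 years for Part C after Amendment 7. SAP 2.4 still gives 2 years for Part C.

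**Relapse.** The objectives tie it to MRI, with no threshold. The re-dosing condition in Protocol 5.5.5.2 begins "Symptoms (pain, swelling, redness, stiffness) and" and adds a volume criterion.

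**The concern.** Whether the drug can replace surgery, and for how long, is the study's stated clinical aim. These two endpoints speak to it most directly.

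A summary of times among patients who had the event leaves out everyone followed for 1.5 to 2 years without one, and those are the patients who show durability. It also depends on how long each patient was watched, which differs between Parts and within Part C. A listing avoids the bias only by estimating nothing.

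The relapse wording is a separate problem. If the analysis sections do not say what counts as relapse, an asymptomatic regrowth on MRI could be counted or not, and the choice could be made after the data are seen.

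**Working it through.** **Inputs.** The plan states no figure for either endpoint (Protocol 9.14 is marked not applicable), so there is nothing to reproduce.

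- Patients exposed to MCS110: 11 in Part B and 18 in Part C (Protocol Section 1, Study CMCS110X2201).
- Follow-up τ: 24 or 18 months (Protocol 3.2.1, 3.2.3). The schedules count four-week months; month 18 is week 72.
- Visit spacing: 3 months in Part B (Protocol 3.2.1), 4 months in Part C (Protocol 3.2.2).
- MRI variability: up to 10% (Protocol 9.13).
- **Assumed:** exponential event times, complete follow-up to τ, and a proportion P of 10% to 70% with the event by month 24.

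**Step 1: event-only mean against mean event-free time within follow-up.** With λ = −ln(1−P)/24:

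- event-only mean = 1/λ − τ·exp(−λτ)/(1−exp(−λτ))
- restricted mean event-free time = (1−exp(−λτ))/λ

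For P = 30%, 1/λ = 67.3 months. At τ = 24 the event-only mean is 67.3 − 24×0.70/0.30 = 67.3 − 56.0 = 11.3, and the restricted mean is 0.30×67.3 = 20.2.

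| P by month 24 | Event-only, τ=24 | Restricted mean, τ=24 | Event-only, τ=18 | Restricted mean, τ=18 | Event-free at 18 |
|---|---|---|---|---|---|
| 10% | 11.8 | 22.8 | 8.9 | 17.3 | 92.4% |
| 30% | 11.3 | 20.2 | 8.6 | 15.8 | 76.5% |
| 50% | 10.6 | 17.3 | 8.2 | 14.0 | 59.5% |
| 70% | 9.6 | 14.0 | 7.7 | 11.9 | 40.5% |

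The event-only mean is short by 4.4 to 11.0 months at τ = 24 and by 4.2 to 8.4 at τ = 18. It also hardly responds to what matters: as the event-free proportion at 24 months falls from 90% to 30%, it moves by only 11.8 − 9.6 = 2.2 months.

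**Step 2: effect of follow-up alone.** With identical hazards, patients followed for 18 months look worse than those followed for 24 by 11.8 − 8.9 = 2.9 months at P = 10%, falling to 9.6 − 7.7 = 1.9 at P = 70%.

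**Step 3: does Kaplan-Meier work at this size?** In 20,000 simulated trials at P = 10, 30 and 50%, the mean Kaplan-Meier restricted mean was 22.8, 20.2 and 17.3 months (n = 11, τ = 24) and 17.3, 15.8 and 14.0 (n = 18, τ = 18). These equal the true values. At P = 10% and n = 11, 31% of trials had no event, so an event-only summary would not exist.

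**Step 4: visit-based detection.** Detecting relapse only at 3- or 4-monthly visits moves recorded times later by about 1.5 to 2 months. That offsets a small part of the shortfall.

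**Step 5: precision of the alternative.** Pooling 11 + 18 = 29 patients followed to month 18 at P = 30%, the standard error is √(0.765×0.235/29) = 0.079, a 95% half-width of about 15 points. In an arm of 6 it is √(0.765×0.235/6) = 0.173, about 34 points.

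**Step 6: the relapse wordings side by side.**

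| Place | What relapse requires |
|---|---|
| Protocol 2.5, 2.8 | MRI, no threshold |
| Protocol Figure 3-2 legend | MRI together with symptoms |
| Protocol 5.5.5.2, re-dosing | Symptoms, plus regain of more than 50% of the lost volume |
| Protocol 9.5.1, SAP 7.2.8 | Recurrence or growth of residual tumor, no threshold |

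After a 50% reduction, the re-dosing rule needs regrowth from 50% to 75% of baseline, a 50% rise over the lowest volume. After 45% the rise is 22.5/55 = 41%, and after 80% it is 40/20 = 200%. Growth with no threshold has to be read against Protocol 9.13's own residual error for a log ratio of two scans, 0.1×√2 = 0.14.

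**The case against.** A reader might infer that the plan will answer both objectives with times that are too short. The documents do not support that. The SAP plans listings, which estimate nothing and so cannot be biased. Only the protocol mentions summarising, firmly for surgery and optionally for relapse. It also presents the number operated on, so a crude proportion without surgery is available, and SAP 7.1 lists tumor volumes at every MRI to the end of the study.

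A reader might also think that the competing relapse wordings shorten times. They do not. Adding a symptom requirement can only date relapse later, or not at all. The symptoms-plus-volume rule is a re-dosing condition, not a stated endpoint definition.

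Nor is it fair to set event-only times against a median of several years. At low event rates the median lies beyond all follow-up, and Kaplan-Meier would rarely reach it. The comparison above therefore stays within follow-up.

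Arms in Part C are about 3 to 10 patients and no power is claimed, so listings by arm are defensible. That stands, and it is why the proposal pools. Finally, blacked-out text follows the relapse paragraphs in both documents, so for relapse only the visible text can be judged. No such mark separates the surgery text from the relapse text that follows it.

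What remains is the absence of any rule for patients without an event, the mismatch between protocol and SAP, and the undefined relapse endpoint.

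**Conclusion.** The point holds in limited form and is minor for a small exploratory study. A summary done as Protocol 9.5.1 states would be biased short, by about 4 to 11 months against the restricted mean under the assumed rates, and would mostly reflect length of follow-up. Done as the SAP states, neither objective gets an estimate. These sizes rest on an exponential shape and event rates that the documents do not give. The direction does not depend on the rate: the event-only mean was below the restricted mean at every rate tried.

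The relapse endpoint lacks an operational definition. The consequence is ambiguity about which patients count and when, with no implied direction of bias.

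The time origin also needs settling. SAP 7.2.7 starts at the first dose, which is placebo for Part B group 2, four weeks before their first MCS110. SAP 7.1 starts time to ablation at the first MCS110 dose.

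**What to change.** Replace the event-only summary in the SAP, and align Protocol 9.5.1 with it:

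- Estimate the event-free proportion for each endpoint by Kaplan-Meier, pooled over MCS110-treated patients in Parts B and C, at fixed times with numbers at risk and confidence intervals. Months 6, 12 and 18 would serve, defined as schedule weeks 24, 48 and 72 because Amendment 7 follow-up ends at week 72.
- Keep results by Part and arm as listings, and add each patient's follow-up time, including those without an event.
- Measure both times from the first MCS110 dose.
- Censor at the last evaluable MRI for relapse and at last contact for surgery, and state how surgery before relapse is handled.
- Reconcile the relapse passages into one definition for the endpoint. It should say whether symptoms are required, what volume change counts and against which scan. The re-dosing rule stays as it is.
- Correct the Part C follow-up in SAP 2.4 to match the protocol.

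The cost is two short SAP paragraphs and a conforming protocol edit. MRI dates, surgery and follow-up are already collected. The downside is that estimates will be imprecise, medians will often not be reached, and the numbers at risk at the last time point may be small.

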9.7 Safety

Vital signs

All vital signs data will be listed by treatment, patient, and visit/time and if ranges are available abnormalities (and relevant orthostatic changes) will be flagged. Summary statistics will be provided by treatment and visit/time.

ECG evaluations

All ECG data will be listed by treatment, patient and visit/time, abnormalities will be flagged. Summary statistics will be provided by treatment and visit/time.

Standard clinical laboratory evaluations

All laboratory data will be listed and graphically displayed by treatment, patient, and visit/time and abnormalities will be flagged. Summary statistics will be provided by treatment and visit/time.

Special clinical laboratory evaluations

All laboratory data will be listed by treatment, patient, and visit/time and if ranges are available abnormalities will be flagged. Summary statistics will be provided by treatment and visit/time.

Confidential

Adverse events

All information obtained on adverse events will be displayed by treatment and patient. The number and percentage of patients with adverse events will be tabulated by body system and preferred term with a breakdown by treatment. An adverse event starting in one period and continuing into the next period is counted only in the onset period. A patient with multiple adverse events within a body system [within a treatment period] is only counted once towards the total of this body system.

Concomitant medications / Significant non-drug therapies

All concomitant therapies will be listed by treatment group and patient.

9.8 Pharmacokinetics

During modeling of the pharmacokinetics of the study drug, the broad principles outlined in the FDA Guidance for Industry: Population Pharmacokinetics will be followed.

For standard pharmacokinetic abbreviations and definitions see the list provided at the beginning of this protocol.

While the serum free MCS110 concentration-time data will mostly be summarized graphically and analyzed using a model-based approach (which will be reported separately in a Modeling & Simulation report), noncompartmental pharmacokinetic analysis will also be performed and the following noncompartmental PK parameters characterizing the disposition of MCS110 will be generated using WinNonlin Phoenix[®] (Version 6.2 or above, Pharsight, Mountain View, CA):

- Part A: AUClast, AUCinf, Tmax, Cmax, CL, Vss, T1/2 and MRT.
- Part B: AUCτ (τ=dosing interval in Part B), Racc (accumulation ratio), Tmax, Cmax, T1/2.
- Part C: AUCτ (τ=dosing interval in Part C), Racc (accumulation ratio), Tmax, Cmax, T1/2.

Additional PK parameters may be determined and compartmental PK modeling may be performed where appropriate.

Biofluid concentrations will be expressed in mass per volume units. All concentrations below the limit of quantification or missing data will be labeled as such in the concentration data listings. Concentrations below the limit of quantification will be treated as zero in summary statistics and for the calculation of pharmacokinetic parameters. Descriptive statistics of pharmacokinetic parameters will include mean, SD, and CV, min and max. When a geometric mean will be presented it will be stated as such. Since T_{max} is generally evaluated by a nonparametric method, median values and ranges will be given for this parameter. Corporate Confidential Information

9.12 PK/PD

Individual serum/plasma concentration versus time profiles of MCS110, M-CSF and other PD biomarkers will be displayed graphically. In addition, PKPD modeling may be performed where appropriate.

The analysis of the relationship between drug concentration and PD variables will be data driven. Therefore, nature of analysis will depend on the type of data obtained in the study and it may be difficult to specify the analysis in advance. Drug concentration-PD data can be evaluated by a PK-PD model (such as target binding model, indirect response model, etc.) analysis if appropriate.

9.13 Sample size calculation

Part A

The trial will be analyzed after each patient has completed Day 28 visit and the tumor volume has been assessed by MRI. The trial may stop at any time if the PoC criterion (see Section 9.4.2) is met, and therefore no fixed sample size is planned. However, a maximum of 12 evaluable patients will be recruited, with a 2:1 ratio MCS110 to placebo. The minimum number of patients to declare PoC is 3, i.e., 2 MCS110 patients and one placebo patient.

Imatinib is known to inhibit the macrophage colony-stimulation factor receptor (CSF-1R). In a recent report it has been demonstrated, that imatinib treatment led to a partial response within 2 months of treatment and a complete response after 5 month of treatment in one case of advanced recurrent PVNS (Blay et al 2008). Given, that imatinib is not a particularly strong inhibitor of CSF-1R (Dewar et al 2005), treatment with an Ab against M-CSF, such as MCS110, which specifically blocks CSF1 signalling is expected to show a 40% reduction in one month.

From scan-rescan MRI reproducibility experiments (Ng et al 2010), it is expected to observe up to 10% variability in measurement of tumor size due to imaging techniques, parameters used, types of tumor (e.g., size or shape) or observers. Due to inter-occasional variability, and due to a potential inflation of variability in the presence of treatment, the actual within-subject variability may be bigger, i.e., the within subject variability in the MCS110 treated patients is assumed to be about twice as much, i.e., 20%. For the placebo patients both 10% and 20% variability assumptions are considered. As a very conservative scenario, we assume also a 30% variability in both groups.

This leads to 3 possible scenarios:

- Scenario 1: 10% within subject variability for the placebo patients and 20% for the MCS110 patients.
- Scenario 2: 20% within subject variability for the placebo and MCS110 patients
- Scenario 3: 30% within subject variability for the placebo and MCS110 patients

Assuming the treatment/placebo effects to be identical in all patients, the residual error of the log ratio relative to baseline is then approximately 0.1 * sqrt(2) or 0.2 * sqrt(2) or 0.3 * sqrt(2), depending on group/scenario.

Novartis	Confidential	Page 136
Amended Protocol Version v07 (Clean)		Protocol No. CMCS110X2201

Given these scenarios, the table below (Table 9-1) summarizes the power of the study obtained by simulations of 800 trials with 4 different sample sizes.

N patients	Scenario 1	Scenario 2	Scenario 3
12	95%	89%	82%
9	90%	85%	79%
6	88%	83%	74%
3	69%	62%	46%

 Table 9-1
 Power estimates for different scenarios

In scenario 1, with 12 patients and assuming a twofold reduction from baseline in tumor size in the MCS110 group as compared to the placebo group, there is about 95% power to reach the PoC criteria as defined above in the analysis section. With 6 patients (4:2), the power is about 88%.

In Scenario 1, the probability to declare a positive PoC when there is no treatment difference is less than 0.6% at each analysis. Therefore the overall type 1 error rate is bounded at 6% (maximum of 10 analyses). In Scenario 2, the overall type 1 error rate is bounded at 9% and in Scenario 3 bounded at 35%.

Part B

There are anticipated to be about 12 patients in Part B (18 in total for this trial). The following table (Table 9-2) presents the 95% Confidence Interval (CI) for the true proportion of patients with complete tumor response, assuming different proportions of patients with complete tumor response are observed.

response							
\hat{p}^{\star}	0/12 (0)	1/12 (0.08)	2/12 (0.17)	3/12 (0.25)	4/12 (0.33)	5/12 (0.42)	6/12 (0.5)
95% CI	(0, 0.22)	(0.002, 0.38)	(0.02, 0.48)	(0.05, 0.57)	(0.1, 0.65)	(0.15, 0.72)	(0.21, 0 .79)

Table 9-295 percent confidence intervals for the proportion of complete
response

p	7/12 (0.58)	8/12 (0.67)	9/12 (0.75)	10/12 (0.83)	11/12 (0.92)	12/12 (1.00)
95% Cl	(0.28, 0.85)	(0.35, 0.90)	(0.43, 0.95)	(0.52, 0.98)	(0.62, 1)	(0.78, 1)

*Note: \hat{p} is the observed proportion of patients with complete tumor response. The proportion is also converted into two decimal places shown in the parenthesis.

Part C

There are anticipated to be 19 patients in Part C (approximately 37 patients in total for the trial). Simulations run using prior study information, log (ratio) of tumor size, and a conservative standard deviation estimate, show that 6 patients per arm in the 3 and 5 mg/kg groups will provide >80% power to declare the lower doses efficacious or not, compared to the 10 mg/kg group.

Confidential

9.14 **Power for analysis of key secondary variables**

Not applicable.

Corporate Confidential Information

10 Ethical considerations

